#### **7.4.2.1.2 Infusion Interruptions/Re-Start/Dosage Adjustments due to Adverse Events**

##### **7.4.2.1.2.1 General Guidelines**

Subjects should be assessed for adverse events at each visit. The severity of the adverse event will be graded using the CTCAE version 5.0 ([Section 12.4](#)), with the exception of CRS, which must be graded using the criteria referenced in the publication by [Lee et al, 2014](#) (see [Table 7-3](#)) and TLS, which must be graded according to the Cairo Bishop criteria referenced in the publication by [Coiffier et al, 2008](#) (see [Section 12.12](#)).

Infusion modification and dose reduction due to an adverse event will be performed according to the instructions described below and outlined in [Table 7-1](#) and [Table 7-3](#).

Infusion interruptions for other reasons need to be discussed with the Amgen medical monitor.

If infusion interruptions of < 14 days occur within a cycle the cycle will be resumed. The counting of the cycle days will not be stopped with an infusion interruption (eg, if the infusion is stopped on cycle day 5 and resumed 5 days later, the day of re-start is cycle day 10).

Following an infusion interruption with < 7 days remaining for infusion after resumption of the cycle, the last treatment days can be skipped and treatment will be continued with the next cycle after a 2-week infusion free interval.

However, treatment should not be given for < 14 days per cycle. An infusion interruption of more than 2 weeks or several interruptions exceeding a total of 14 days of treatment per cycle due to serious adverse events/adverse events require permanent treatment discontinuation.

Please note: the guidance in [Section 7.4.2.1.2](#) does not apply to the treatment holiday described in [Section 7.1.1.2](#).

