≥ Grade 3	Interruption required if Grade 4 event, or if Grade 3 event is deemed intolerable by the subject or investigator and not responding to appropriate medical management until event has improved to grade ≤ 2 (grade ≤ 1 in the case of neurological event)	Neurological examination should be performed before resuming dosing in case the infusion interruption was due to a neurologic event.	
 
• Re-start possible if successfully managed and improvement to grade ≤ 2 in ≤ 14 days.
 
• Hospitalization: 48 hours
 
• Dose modification: resume at the same dose or reduce to next lower dose if clinically indicated (ie, 200 µg/day for subjects originally receiving 400 µg/day or 400 µg/day for those originally receiving 600 µg/day)
 
• Additional measures: additional assessments and premedication as indicated in Sections 7.4.2.1.2.3/7.4.2.1.2.4
 
	
If interruption is > 14 days
 
In case of reappearance of same event at Grade 4

Abbreviations and footnotes defined on last page of table.

**Table 7-2. Additional Guidance on Infusion Interruptions/Permanent Discontinuations and Management of Adverse Events Including Dose Reductions**

	Interruption	Specific Management	Re-Start Guidance	Permanent Discontinuation
Any Non-AMG 420 related events				
Grade 4	Interruption required if Grade 4 event, or if Grade 3 event is deemed intolerable by the subject or investigator and not responding to appropriate medical management until event has improved to Grade $\leq 2$	n/a	
 
Re-start possible if successfully managed and improvement to grade <math>\leq 2</math> in <math>\leq 14</math> days.
 
Hospitalization: 48 hours
 
Dose modification: resume at the same dose or reduce to next lower dose if clinically indicated (ie, 200 <math>\mu\text{g/day}</math> for subjects originally receiving 400 <math>\mu\text{g/day}</math> or 400 <math>\mu\text{g/day}</math> for those originally receiving 600 <math>\mu\text{g/day}</math>)
 
Additional measures: additional assessments and premedication as indicated in Sections 7.4.2.1.2.3/7.4.2.1.2.4
 
	
If interruption is > 14 days
 
In case of reappearance of same event at Grade 4

Abbreviations and footnotes defined on last page of table.

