SARS-CoV2 infection and COVID19 disease				
symptomatic	Interruption required until at least 10 days since complete resolution of acute symptoms	Follow local guidelines and standard of care for COVID-19 treatment and isolation  Contact Amgen Medical Monitor within 1 business day to ensure appropriate documentation & management of study activities.	
 
• Re-start possible upon agreement between Investigator and Amgen Medical Monitor provided:               
 
○ There are no new findings on physical exam and chest imaging, related to SARS-COV-2
 
○ Subject tests negative for SARS-COV-2 by RT-PCR
 
 
 
OR               
 
○ If subject continues to test positive for SARS-COV-2 more than 10 days after initial positive test, resume IP only after discussion with patient and reassessment of individual risk/benefit
 
 
 
• Consider chest imaging, ECG, ECHO, and cardiology assessment 1
 
• Consider hospitalization for re-start of IP based on length of treatment interruption, risk of CRS at restart, and amount of time since patient was last treated 2
 
• Dose modification: resume at the same dose or reduce to next lower dose if clinically indicated
 
• Premedication and assessments: follow guidance in SOA tables
 
	
Immediately stop the infusion (if applicable) and permanently discontinue IP therapy IF
 
Subject required treatment interruption greater than 28 days due to severe or life-threatening COVID-19
 
OR
 
Initial benefit/risk assessment for individual patient is not maintained any longer

Product: AMG 420  
Protocol Number: 20160370  
Date: 17 September 2021

Page 74 of 169

---

CRS = cytokine release syndrome; CTCAE = Common Terminology Criteria for Adverse Events; COVID-19 = coronavirus disease 2019; ECG = electrocardiogram; ECHO = echocardiogram; IP = investigational product; RT-PCR = real time polymerase chain reaction; SARS-COV-2 = severe acute respiratory syndrome coronavirus 2; SOA = Schedule of Activities.

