#### 7.8.2.6 Infections

Prophylactic antibiotics, antifungal, and antivirals are allowed and should be given according to institutional standards. Pneumocystis prophylaxis should also be given according to institutional standards. For subjects who are considered to have an increased risk for herpes infections, prophylaxis is mandatory unless medically contraindicated. Subjects who may experience neutropenia for 7 days or longer are at a high risk for infectious complications. As appropriate, these subjects should be administered prophylactic antibacterial, antifungal, and antiviral medications. These subjects should be monitored for early signs of breakthrough infections after the initiation of antibacterial therapy to prompt additional evaluation and possible therapy modification.

Subjects presenting with evidence of active infection after the start of AMG 420 treatment should be closely monitored while being treated with AMG 420. Subjects with identified, active systemic infections requiring IV antibiotics, antivirals, or antifungals should not be dosed with AMG 420 until infection has resolved, and if being treated with an anti-infectious therapy, the course of such therapy should have been completed.

Patients who develop fever greater than 38.0°C lasting more than 1 hour or fever greater than 38.3°C of any duration during AMG 420 treatment should be promptly evaluated for infection as well as cytokine release syndrome (CRS). Workup should include evaluation for bacterial, fungal, and viral etiologies using radiographic imaging and appropriate microbiological/serologic assays, and empiric therapy should be considered using investigator's institutional standard of care approach. Guidelines for dose interruption and AMG 420 discontinuation as detailed in [Tables 7-1](#) and [7-2](#) should be followed. Investigators should consider the potential immunosuppressive effects of CRS rescue medications (eg, tocilizumab, corticosteroids) in their empiric management of fever. If patients develop febrile neutropenia (defined as ANC < 1000 10^6/L with a single temperature of > 38.3°C [101°F] or a sustained temperature of ≥ 38°C [100.4°F] for more than one hour), use of standardized guidelines for management and initial treatment of neutropenic fever (eg, Infectious Diseases Society of America Clinical Practice Guidelines, Management of Febrile Neutropaenia: ESMO Clinical Practice Guidelines) is encouraged.

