#### **9.1.2 Treatment Period**

Visits will occur per the Schedule of Activities ([Section 2.2](#)). The date of the first dose of investigational product is defined as day 1. All subsequent doses and study visits will be scheduled based on the day 1 date. Administration of AMG 420 is to be administered as applicable during each visit that it is required.

Starting with day 4 post infusion, assessments should be performed on the indicated study day, but not at a certain hour of the day. The D6 sample may also be taken on D7 if logistically required (eg, sample cannot be processed at the weekend). Bone marrow assessments post-treatment start may be performed within a window of  $\pm 3$  days. Visits during treatment-free interval, if applicable, may occur within a window of  $\pm 1$  day.

Furthermore, start of a treatment cycle can be delayed for administrative/logistical reasons for up to 7 days to allow for appropriate scheduling. **Start of treatment cycles later than 7 days from planned next cycle day 1 must only occur** after discussion with and final approval by sponsor. **Delays of treatment cycles beyond 14 days are not permitted.**

The DLRT may implement a  $\pm$  1-day window for infusions following the day 1 infusion.

In any case of premature treatment discontinuation prior to day 29 (EOI) the assessments for day 29 do not have to be performed, but the investigator should make every effort to perform all examinations scheduled for the EOT (see [Section 2.2](#)).

The expected treatment period is to treat until PD per IMWG (or other protocol-specific reasons as per [Section 8.1](#)).

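### The COVID-19 restart rule in Table 7-2 conflicts with the protocol's 14-day limits, and the infection hold in Section 7.8.2.6 is not aligned with Table 7-2 or with those limits

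*Protocol*

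**What the plan says.** **COVID-19 rows of Table 7-2 (Protocol).** For symptomatic disease: "Interruption required until at least 10 days since complete resolution of acute symptoms". Permanent discontinuation is listed for "Subject required treatment interruption greater than 28 days due to severe or life-threatening COVID-19", or if the individual benefit/risk is no longer favourable. The asymptomatic row holds unvaccinated subjects for at least 10 days from the positive test. It also uses 28 days as its stop threshold, and only after discussion with the medical monitor.

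**14-day limits.** Section 7.4.2.1.2.1 says that "An infusion interruption of more than 2 weeks or several interruptions exceeding a total of 14 days of treatment per cycle" due to adverse events requires permanent discontinuation, and the list in Section 7.4.2.1.3 repeats this. For late cycle starts, Section 9.1.2 says "Delays of treatment cycles beyond 14 days are not permitted"; the same sentence stands in Section 7.4.2.1.2.2 on delays due to adverse events. The only exception stated in 7.4.2.1.2.1 is the treatment holiday.

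**Other infections.** Section 7.8.2.6 first says: "Subjects presenting with evidence of active infection after the start of AMG 420 treatment should be closely monitored while being treated with AMG 420". For systemic infection needing IV antibiotics, antivirals or antifungals, it says subjects "should not be dosed with AMG 420 until infection has resolved, and if being treated with an anti-infectious therapy, the course of such therapy" must be complete. Its next paragraph, on fever work-up, tells sites to follow "Guidelines for dose interruption and AMG 420 discontinuation as detailed in" Tables 7-1 and 7-2. The general rows of Table 7-2 read: "Interruption required if Grade 4 event, or if Grade 3 event is deemed intolerable by the subject or investigator and not responding" to medical management. They allow restart once the event is grade 2 or lower within 14 days, and they require a permanent stop if the interruption exceeds 14 days.

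**The concern.** For some COVID-19 episodes the stopping instructions cannot all be followed. One text makes discontinuation mandatory, while another treats the subject as eligible to restart. For other infections the texts can be followed together at onset, but they differ on when drug may be resumed. Section 7.8.2.6 is also silent on what happens when its own hold passes 14 days.

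Infection is one of the three key risks in Table 3-1, so these rules are likely to be used. The consequences are:

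- **Patient safety.** Staff may act on different instructions for the same event.
- **Primary safety data.** SAP Section 9.6.2 tabulates adverse events leading to interruption and to withdrawal. With about 10 subjects per dose level, one subject handled differently moves a rate by 1/10, or 10 percentage points.
- **DLT set.** A cycle 1 stop for a non-DLT reason makes a subject non-evaluable and replaceable (Protocol Sections 5.2.1 and 7.4.1).
- **Exposure.** Cumulative dose and number of cycles depend on which rule is applied.

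**Working it through.** **1. The rules side by side**

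| Situation | Table 7-2 | Other sections |
|---|---|---|
| Symptomatic COVID-19 | Hold to symptom resolution + 10 days; time-based stop only beyond 28 days, for severe or life-threatening disease | 7.4.2.1.2.1 and 7.4.2.1.3: stop if interruption > 14 days. 7.4.2.1.2.2 and 9.1.2: no cycle delay > 14 days |
| Asymptomatic SARS-CoV-2, unvaccinated | Hold at least 10 days; stop considered beyond 28 days | Same limits, if handled as an adverse event |
| Systemic infection on IV therapy | Interruption required for grade 4, or grade 3 that is intolerable and not responding; restart at grade ≤ 2; stop if > 14 days | 7.8.2.6: hold until resolved and course complete; no grade or time limit |

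**2. Length of a symptomatic COVID-19 hold**

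Assume the infusion stops at symptom onset, and let S be the days of symptoms. The minimum hold is H = S + 10.

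- S = 4: H = 14, within the limit.
- S = 5: H = 15, over 14.
- S = 18: H = 28, the last value not beyond the Table 7-2 threshold.

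Holds of 15 to 28 days (S = 5 to 18) can therefore fall between the two thresholds. Longer holds can too, if the disease is not severe or life-threatening.

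**3. Whether the limit is actually passed depends on onset day**

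The infusion runs from day 1 to its end on day 29. The infusion-free interval is days 30 to 42, and day 43 is day 1 of the next cycle (Table 2-1, footnote a). For onset on cycle day t:

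- Infusion days lost = min(H, 29 − t). With H = 15, this exceeds 14 only if 29 − t ≥ 15, that is t ≤ 14. On day 14 the loss is 15 days; on day 15 it is 14.
- Delay of the next cycle = t + H − 43. With H = 15 and t = 30 to 42, the delay is 2 to 14 days, within the limit.
- In the infusion-free interval the delay passes 14 days when H > 57 − t. At t = 42 this needs H ≥ 16; at t = 30 it needs H ≥ 28.

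So a 15-day hold breaches a limit for onset on about days 1 to 14. Onset on days 15 to 29 with H ≤ 28 stays within both limits. Onset in the infusion-free interval breaches the delay limit only with a longer hold.

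**4. Infection on IV therapy**

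The minimum hold under 7.8.2.6 is the length of the anti-infective course, which the documents do not give. A course of 14 days or less stays within the limit, and only the hold and restart conditions differ. A course of 15 days or more (an assumption) can pass the limit, and 7.8.2.6 does not address that case.

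**5. Likely frequency**

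The plan gives no figure for this point. Its formula for seeing at least one event reproduces: 1 − 0.9^10 = 65% and 1 − 0.8^10 = 89%, as in Protocol Section 10.1.

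Section 3.2.2.4 reports serious device-related infections in 3 of 35 first-in-human subjects (8.6%). For 20 subjects:

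- Expected: 20 × 3/35 = 1.7.
- At least one: 1 − (32/35)^20 = 0.833, about 83%.

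Three events give little precision. The exact (Clopper-Pearson) 95% interval for 3/35 is 1.8% to 23.1%. The chance of at least one in 20 then runs from 1 − (1 − 0.018)^20, about 31%, to 1 − (1 − 0.231)^20, about 99%.

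**The case against.** **The COVID-19 rows are specific and should override the general limit.** This is the strongest defence. Table 7-1 already departs from 14 days for neurotoxicity (up to 28 days if approved) and for tumor lysis syndrome (on consultation). The COVID-19 rows require contact with the medical monitor within 1 business day, and restart needs the monitor's agreement, so divergence between sites would be limited. That reading is reasonable, but no text states it. Section 7.4.2.1.2.1 names only the treatment holiday and points to Tables 7-1 and 7-3, not 7-2. Section 7.4.2.1.3 repeats the limit without a COVID-19 exception. Amendment 5 lists both the COVID-19 table and the delay clarifications, yet no link between them was written.

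**Table 7-2 does not order continued infusion.** This stands. A reader might infer that a responding grade 3 line infection must stay on drug under Table 7-2. The general rows set minimum triggers for interruption, so a site that holds under 7.8.2.6 breaches nothing. The pointer to the tables also sits in the fever paragraph, not in the sentence on systemic infection.

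**Other stronger readings fail.**

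- A reader might infer that symptomatic COVID-19 can lead to continued infusion, restart or permanent stop. The symptomatic row requires interruption; the conflict is between restart and permanent stop.
- A reader might infer that every episode with 5 or more symptomatic days breaches the limit. Onset later in the cycle or in the infusion-free interval may not.
- A reader might take all device-related infections (7/35, 20.0%), giving 4 expected in 20 and a 99% chance of at least one. That count is not restricted to infections needing a hold.
- A reader might infer direct bias in PFS or DOR. Stopping drug is not a censoring event in SAP Table 2, and subjects without progression are assessed every 6 weeks (Protocol Section 9.1.5). Any effect would come through later therapy and is not quantified.

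**Conclusion.** The concern holds in two parts.

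1. **Contradiction.** A symptomatic COVID-19 interruption of more than 14 infusion days and up to 28 days is a possible restart under Table 7-2 and a mandatory stop under Sections 7.4.2.1.2.1 and 7.4.2.1.3. Five symptomatic days are enough if the infusion stops at onset and onset falls on about cycle days 1 to 14. The 28-day threshold for asymptomatic infection raises the same question if that event is handled as an adverse event.
2. **Misalignment.** Section 7.8.2.6 and the general rows of Table 7-2 can both be met by holding drug. Their triggers and restart conditions differ, however, and 7.8.2.6 does not say how its open-ended hold relates to the 14-day limit.

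COVID-19 frequency cannot be sized from the documents. For infections needing a hold, about 1.7 in 20 subjects and an 83% chance of at least one rest on an imperfect proxy: serious events need not be systemic or need IV therapy, and some non-serious ones may. The point still merits correction before sites rely on these rules, because it concerns mandatory stopping instructions and feeds the tabulated withdrawals.

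**What to change.** Reconcile Protocol Sections 7.4.2.1.2.1, 7.4.2.1.2.2, 7.4.2.1.3, 7.8.2.6 and 9.1.2 with Table 7-2:

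- State in the sections that carry the 14-day limits whether the SARS-CoV-2 rows are an exception to the interruption limit, the cycle-delay limit, both or neither.
- Cross-reference 7.8.2.6 and Table 7-2, for example through a dedicated infection row, so that one hold, restart and stop rule appears everywhere.
- State how that rule relates to the 14-day limit, including when an anti-infective course runs longer.

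Which rule applies is the sponsor's clinical decision; this review takes no position on it. The cost is an amendment or clarification letter and a site memo, with no added subjects or procedures.

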### 7.8.2.7 Tumor Lysis Syndrome

Tumor Lysis Syndrome is a severe, life-threatening disorder that typically occurs in highly proliferative malignancies. Tumor Lysis Syndrome is frequently observed in patients with hematologic malignancies such as ALL and Burkitt's lymphoma. Tumor Lysis Syndrome is rarely reported in patients with multiple myeloma although patients with a high tumor burden may be at greater risk for TLS ([Chang et al, 2011](#); [Cairo et al, 2010](#)). However, given effective new treatments are now available TLS incidence has been reported to be  $\leq 5\%$  in patients with multiple myeloma who received different treatments ([Howard et al, 2016](#)). Tumor Lysis Syndrome is characterized by a group of metabolic disorders caused by the massive and abrupt release of cellular metabolites into the blood including lactate dehydrogenase (LDH), uric acid, phosphorus, potassium, and calcium after lysis of the malignant cells ([Coiffier et al, 2008](#)). The metabolic complications predispose patients with cancer to various clinical complications included renal failure, seizures, cardiac arrhythmias, and even sudden death. To allow for early diagnosis all subjects must be monitored closely for laboratory and clinical evidence of a possible TLS as outlined in [Section 12.12](#) of the protocol.

To prevent TLS, ensure all subjects are well hydrated and provided supportive care measures before administration of AMG 420 as detailed in [Section 7.8.2.1](#). Monitor for evidence of TLS during treatment and manage promptly including interruption of AMG 420 infusion as outlined in [Table 7-1](#). Subjects who experience TLS should be managed according to the local standard of care and institutional guidelines. Supportive therapy, including rasburicase, may be used as clinically indicated at the investigator's discretion.

## 8. Discontinuation Criteria

Subjects have the right to withdraw from investigational product and/or other protocol-required therapies, protocol procedures, or the study as a whole at any time and for any reason without prejudice to their future medical care by the physician or at the institution.

The investigator and/or sponsor can decide to withdraw a subject(s) from investigational product, device, and/or other protocol-required therapies, protocol procedures, or the study as a whole at any time prior to study completion for the reasons listed in [Sections 8.1, 8.2.1, and 8.2.2](#).

## 8.1 Discontinuation of Study Treatment

Subjects (or a legally acceptable representative) can decline to continue receiving investigational product and/or other protocol-required therapies or procedures at any time during the study but continue participation in the study. If this occurs, the investigator is to discuss with the subject the appropriate processes for discontinuation from investigational product or other protocol-required therapies and must discuss with the subject the possibilities for continuation of the Schedule of Activities (see [Section 2.2](#)) including different options of follow-up (eg, in person, by phone/mail, through family/friends, in correspondence/communication with other treating physicians, from the review of medical records) and collection of data (including endpoints, adverse events, and serious adverse events) and must document this decision in the subject's medical records. Subjects who have discontinued investigational product and/or other protocol-required therapies or procedures should not be automatically removed from the study. Whenever safe and feasible, it is imperative that subjects remain on-study to ensure safety surveillance and/or collection of outcome data.

Subjects may be eligible for continued treatment with Amgen investigational product(s) and/or other protocol-required therapies by a separate protocol or as provided for by the local country's regulatory mechanism, based on parameters consistent with [Section 12.3](#).

Reasons for removal from protocol-required investigational product(s) or procedural assessments include any of the following:

- Decision by Sponsor
- Lost to follow-up
- Death
- Ineligibility determined
- Protocol deviation
- Non-compliance
- Adverse event
- Subject request
- Disease progression, based on IMWG criteria, in which confirmation of progression requires 2 consecutive laboratory evaluations, except in cases in which progression is based on EM or bone lesions. Laboratory assessments should be separated in time by at least 1 calendar day
- Requirement for alternative therapy
- Pregnancy

